### 10.2 Placebo

A placebo identical in appearance to rosuvastatin will be produced by Pharmaceutical Packaging Professionals (PPP) in Thebarton South Australia. Stability tests will be performed by PPP and lot numbers and expiry dates provided to the sites.

### 10.3 Packaging and Labelling

Packaging and labelling will be in accordance with the applicable local regulatory requirements.

The study medication will be packed into bottles by Pharmaceutical Packaging Professionals (PPP) and shipped to the sites.

Labels will contain the following information: “for clinical trial use only”; study name and number; lot number, expiry date or re-testing date; patient ID or randomization number; “keep out of reach of children”; storage condition; name of PI and Institution.

The study medication will be distributed to the patient by the local research investigator or study nurse.

#### 10.4 Timing of dosing

Rosuvastatin is taken once daily and can be taken with or without food. Participants will be encouraged to take it at the same time every day with a glass of water. Catch up doses should NOT be taken in the setting of a missed/forgotten dose.

#### 10.5 Storage

The study medication should be stored in its provided packaging at room temperature (<30°C) away from heat and moisture.

#### 10.6 Drug Accountability

The Investigator is responsible for ensuring accountability for the study medication, including reconciliation of drugs and maintenance of drug records.

Drug accountability documentation will be performed according to the local regulatory requirements and will include confirmation of the study medication received at the site; the study medication distributed to the patient and returned by the patient; lost or destroyed study medication; corresponding dates, quantities, batch numbers, expiry dates, as well as subject identification numbers.

The investigator should maintain records that adequately document:

- That the subjects were provided the doses specified by the protocol/amendment(s)
- That all study medication provided to the site was fully reconciled.

#### 10.7 Compliance assessment

Compliance to the study medication (rosuvastatin and placebo) will be assessed by self-reported questionnaire using a modified Medication Adherence Self-Report Inventory and visual analogue scale (VAS) .

If it appears that a participant is not taking the study medication according to protocol they will be counselled by the investigator in an attempt to improve compliance.

#### 10.8 Warnings and precautions

##### **Musculoskeletal reported side effects**

HMG-CoA reductase inhibitors (statins) have been associated with rare cases of severe myopathy and rhabdomyolysis, accompanied by increases in creatine kinase (>10x upper normal limit), myoglobinuria, proteinuria, and renal failure, mainly observed in 40mg daily dosage. Concomitant use with gemfibrozil (fibrin acid derivatives), niacin, cyclosporine, erythromycin (macrolides) or azole antifungals may increase the incidence and severity of musculoskeletal side effects. Milder forms of myotoxicity (i.e., myalgia) are commonly reported and occur in approximately 5% to 7% of patients taking a statin drug.

### 10.9 Concomitant medications

Participants are not to commence any new medication without notifying the study coordinators to allow an assessment for potential interactions with the study medication.

#### 10.9.1 Contraindications

The use of rosuvastatin is contraindicated in combination with the following medications. A patient requiring commencement of these medications following enrolment will be withdrawn from the study.

- Cyclosporine
  - o Combined uses significantly increases rosuvastatin exposure.
- Gemfibrozil and other fibrates
  - o Combined use increases the risk of adverse skeletal muscle effects and should only be used with caution
- Niacin
  - o Combined use increases the risk of adverse skeletal muscle effects and should only be used with caution
- Fusidic acid
  - o Combined use increased rosuvastatin levels and the risk of adverse skeletal muscle effects

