### 9.4 Removal of participants from therapy/assessment

Participants will be withdrawn from the trial if:

1. A SAE occurs which is thought to be related to involvement in the study
2. The subject withdraws consent
3. The subject becomes pregnant
4. The subject is diagnosed with clinical cardiovascular disease
  - a. Cardiovascular
    - i. Acute myocardial infarction (AMI)
    - ii. Development of angina
    - iii. New ECG changes consistent with cardiovascular disease
  - b. Cerebrovascular
    - i. Stroke or Transient Ischaemic Attack (TIA)
  - c. Peripheral vascular disease
    - i. Symptomatic claudication
5. The subject is diagnosed with an acute serious medical illness that would be a contraindication to statin therapy i.e.
  - a. Acute viral hepatitis ( A, B or C)
6. CK or transaminase elevation (> 3 times)

7. Subject is judged by the investigator to be at significant risk of failing to comply with the provisions of the protocol so as to cause harm to self or seriously interfere with the validity of the study result.

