### 9.5 Pregnancy

Women of child-bearing potential will be screened for pregnancy on admission to the study. Due to a lack of study data relating to the effects of statins on pregnant woman and/or the foetus those who are found to be pregnant will be excluded from study participation and referred to an appropriate medical service.

Female participants will be advised to avoid pregnancy while participating in the study. Women who become pregnant after randomisation will be withdrawn from the trial but will continue to be monitored for the development of adverse events (AE) or serious adverse events (SAE).

*For Switzerland: Women of childbearing potential must use two reliable contraceptive methods during the entire trial, from day 1 to one month after the end of the trial. Accepted methods are hormonal methods such as the birth control pill associated with a barrier method such as the preservative.*

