#### 10.9.3 Antiretrovirals

Participants must be on a stable ARV regimen for  $> 3$  months (with HIV viral load  $< 200$  for  $> 6$  months) to be eligible for acceptance into the study. ARV regimens will remain at the

discretion of the patients treating physician who will be blinded to study medication but not involvement in the study.

Participants on any PI-based cART regimen will receive 1 x 10 mg rosuvastatin (effective exposure 20 mg daily).

Participants who require a change in antiretroviral regimen following randomisation on the basis of treatment failure or intolerability (that could not be attributed to the study medication) may remain within the study.

- Patients who switch from a PI containing regimen to a non-PI containing regimen will have the dose of rosuvastatin (or placebo) increased to 20mg daily
- Patients who switch from a non-PI containing regimen to a PI containing regimen will have the dose of rosuvastatin (or placebo) reduced to 10mg daily
- Switches within classes of ARV require no change in study medication dose

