### **12.1 Withdrawal visit**

For participants that fulfil any of the withdrawal criteria above a withdrawal visit is performed if the participant agrees. All assessments made during the withdrawal visit can be recorded on the CRF (unscheduled visit). This visit will include, but is not limited to, a targeted medical review and physical examination, laboratory examination for safety reasons (chemistry and haematology), pregnancy test for women and study drug return. Tests performed can vary according to the judgement of the study physician.

Clinical or biological abnormalities perceived at the withdrawal visit will be followed at an interval decided by the study physician, until they are resolved or baseline values obtained.

Participants that withdraw from the study may be contacted by telephone at study end for vital status, unless they refuse and this is documented.

In Australia: In the event of withdrawal of consent by the participant, the Form for withdrawal of participants is completed.

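### Medical withdrawal rules take participants out of the study, not only off study drug, so scheduled cIMT is likely lost for reasons that may depend on treatment or disease

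*Combined protocol and SAP*

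**What the plan says.** - **Section 10.9.1** lists cyclosporine, fibrates, niacin and fusidic acid as contraindicated with rosuvastatin and adds: "A patient requiring commencement of these medications following enrolment will be withdrawn from the study". Under fibrates and again under niacin it comments: "Combined use increases the risk of adverse skeletal muscle effects and should only be used with caution".
- **Section 9.4** withdraws participants from the trial for, among other reasons, a study-related SAE, new clinical cardiovascular disease, and "CK or transaminase elevation (> 3 times").
- **Section 11.3** withdraws from the study anyone found to have a significant carotid plaque.
- **Section 12.1, Withdrawal visit** (the second section with that number) describes what follows, if the participant agrees to a visit: "This visit will include, but is not limited to, a targeted medical review and physical examination", plus safety bloods, a pregnancy test for women and drug return. Other tests are left to the study physician. Abnormal findings "will be followed at an interval decided by the study physician, until they are resolved or baseline values obtained". Finally, "Participants that withdraw from the study may be contacted by telephone at study end for vital status". No cIMT is listed.
- **Section 9.5** is the one place that specifies continued monitoring for a withdrawn group, and it is for safety: "Women who become pregnant after randomisation will be withdrawn from the trial but will continue to be monitored for the development of adverse events" or serious adverse events.
- **Section 10.9.3** treats another post-randomisation drug change differently. Participants who change antiretrovirals because of treatment failure or intolerance ("that could not be attributed to the study medication) may remain within the study", with the study dose adjusted if a protease inhibitor is started or stopped.
- **Section 17** analyses efficacy by randomised group whatever treatment was taken, among those with randomisation data and at least one follow-up visit. It carries the last value forward in the primary analysis for anyone permanently lost to follow-up.

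**The concern.** An intention-to-treat estimate that disregards treatment received is only as good as the outcomes collected after treatment changes. Here several medical events end participation itself, and nothing afterwards schedules the primary measurement.

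The reasons are not neutral. CK or transaminase elevation may be an effect of rosuvastatin. New clinical cardiovascular disease and significant plaque belong to the disease process that cIMT is meant to track. Starting a fibrate or niacin may reflect worsening lipids. Missing cIMT from these causes may therefore be related to arm or to progression.

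If such a participant is then handled by carry-forward, the imputed change stops at the last scan. For someone with only the screening scan, that means zero progression. In a placebo participant who was in fact progressing, this pulls the comparison toward no difference. Section 17 does not say whether a protocol-driven withdrawal counts as permanent loss to follow-up, so the handling is also open.

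**Working it through.** **Inputs.** From section 6.6: 0.080 mm progression over 2 years on placebo; 95% relative reduction, so 0.080 × 0.05 = 0.004 mm on rosuvastatin; difference 0.076 mm; SD 0.09 mm; alpha 1%; 90% power; 44 per group; 102 in total. Allocation is 1:1 (section 12.4), so 102/2 = 51 per arm. Assumptions: two-sided test (sidedness is not stated), linear progression, and a two-sample t-test on change, as in the plan's own sample-size calculation. The documents give no rate for any of these withdrawals, so the results are per participant.

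**The plan's figure.** Standardised effect 0.076/0.09 = 0.844. The two-sided t-test at alpha 1% and 90% power needs 43.4, so 44 per group, as stated. Power is 90.5% at 44 per arm and 94.7% at 51 per arm.

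**Shift in the difference per participant carried forward** (lost progression ÷ number in the arm):

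| Case | Shift | Share of 0.076 mm |
|---|---|---|
| Placebo, screening cIMT only | 0.080/51 = 0.0016 mm | 2.1% |
| Placebo, last cIMT at week 48 | 0.040/51 = 0.0008 mm | 1.0% |
| Rosuvastatin, screening cIMT only | 0.004/51 = 0.0001 mm | 0.1% |
| Excluded from the analysis set instead | 0 in expectation | 0% |

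The 0.0016 mm is an upper bound. The participant must be in the analysis set, must be counted as permanently lost, and must otherwise have progressed the full 0.080 mm. Someone who would have progressed half as far gives 0.040/51 = 0.0008 mm.

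**Power with k of 51 placebo participants scored as zero change.** With p = k/51, the placebo mean is 0.080(1 − p) and the placebo variance is (1 − p)·0.09² + p(1 − p)·0.080². The rosuvastatin arm is unchanged.

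| k | Difference | Power, carried forward | Power, excluded |
|---|---|---|---|
| 0 | 0.0760 mm | 94.7% | 94.7% |
| 1 | 0.0744 mm | 93.8% | 94.5% |
| 2 | 0.0729 mm | 92.7% | 94.2% |
| 5 | 0.0682 mm | 88.7% | – |

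Five is an illustration, not a forecast: it shows how many early placebo withdrawals, all at the upper bound, would bring power below 90%.

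**Sensitivity.** These powers assume that 51 per arm are analysed with no other losses. If other drop-out left 44 per arm, the upper bound per participant would be 0.080/44 = 0.0018 mm (2.4%). Power would then go from 90.5% to 88.9% (k = 1) and 87.1% (k = 2), by the same formula with 44 in place of 51.

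**The case against.** Several stronger readings are tempting, and the documents do not support them.

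- **That section 10.9.1 permits what it forbids.** A reader might infer this from the caution wording under fibrates and niacin. The clause sits in a sub-bullet that gives the reason for listing the drug, beneath an explicit contraindication and withdrawal rule. It is clumsy wording and not a permission; a site would probably follow the rule. Section 10.9 also requires coordinators to be told before any new medicine is started.
- **That section 17 promises cIMT after withdrawal.** It does not. Its wording governs how participants are grouped, and it provides carry-forward for those lost. The mismatch is with what such an analysis needs, not with a stated commitment.
- **That withdrawal rules out further cIMT.** The withdrawal visit is open-ended and tests vary with the physician's judgement. The loss is a likely consequence of nothing being scheduled.
- **That fibrate or niacin starts threaten the result.** They are probably few: entry excludes people recommended lipid-lowering therapy and those with triglycerides above 4.0 mmol/L (section 9.2), and metabolic results are blinded during the study (section 11.2).
- **That section 10.9.3 is a direct precedent.** There the study dose can be adjusted; no dose is offered for a contraindicated combination. It shows only that a drug change need not end participation.

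Two objections stand. Attrition is already planned for, at 15%. And continued follow-up has a price: participants with new cardiovascular disease or plaque may go onto open-label lipid-lowering therapy, and following them estimates a treatment-policy effect, which can itself shrink the difference. Still, that is the effect an analysis regardless of treatment received is meant to estimate, and it would rest on measured rather than imputed values.

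**Conclusion.** The point holds as a minor one. Sections 10.9.1, 9.4 and 11.3 end study participation where ending study medication would do, and no later cIMT is scheduled. Loss of primary-endpoint data is therefore likely, and for the section 9.4 and 11.3 reasons it may be related to treatment or disease. Those withdrawals carry most of the weight; contraindicated-drug starts alone matter very little.

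The size is at most 0.0016 mm (2.1%) per early placebo participant carried forward, and it may be zero. One or two such participants leave power at 92.7% or more with 51 per arm analysed. The case for change is avoidable, possibly informative missing data, not a shortfall in power. This rests on section 6.6's progression and SD, linear progression, a two-sided test, and an unknown number of events.

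**What to change.** 1. In section 10.9.1, in section 9.4 for the medical reasons, and in section 11.3, replace withdrawal from the study with: *study medication is stopped; scheduled visits and week 48 and 96 cIMT continue where safe unless consent is withdrawn.*
2. In section 13, where the 4-week limit applies to interruptions for suspected toxicity, state that a longer interruption ends study medication and not follow-up.
3. As a tidy-up, delete the caution clause at the end of the comments under fibrates and niacin in section 10.9.1, leaving the contraindication as the only rule.

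No new procedure, form or type of visit is needed. A few participants would attend while off study drug, for a 20-minute ultrasound that section 11.3 describes as painless and harmless. Some may by then be on open-label lipid-lowering therapy, which can dilute the difference under a treatment-policy analysis.

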#### 10.9.2 Warfarin

Combined use of coumarin anticoagulants with rosuvastatin is not contraindicated but will lead to prolonged INR. Patients should have a stable INR prior to starting rosuvastatin. INR monitoring should occur at increased frequency upon initiation or alteration of rosuvastatin dose.

#### 10.9.3 Antiretrovirals

Participants must be on a stable ARV regimen for  $> 3$  months (with HIV viral load  $< 200$  for  $> 6$  months) to be eligible for acceptance into the study. ARV regimens will remain at the

discretion of the patients treating physician who will be blinded to study medication but not involvement in the study.

Participants on any PI-based cART regimen will receive 1 x 10 mg rosuvastatin (effective exposure 20 mg daily).

Participants who require a change in antiretroviral regimen following randomisation on the basis of treatment failure or intolerability (that could not be attributed to the study medication) may remain within the study.

- Patients who switch from a PI containing regimen to a non-PI containing regimen will have the dose of rosuvastatin (or placebo) increased to 20mg daily
- Patients who switch from a non-PI containing regimen to a PI containing regimen will have the dose of rosuvastatin (or placebo) reduced to 10mg daily
- Switches within classes of ARV require no change in study medication dose

### 10.10 Drug interactions listm

Table below: Influence of concomitantly administered drugs on exposure to rosuvastatin (AUC, Cmax in descending order of effect size) based on published clinical trials. Source: Swiss Compendium (www.compendium.ch)

Interacting Drug, dosage and treatment period	Rosuvastatin-dosage and treatment period	Effect on rosuvastatin AUC	Effect on rosuvastatin-C max
Ciclosporin 75 mg b.i.d. up to 200 mg b.i.d., 6 Months	10 mg q.d., 10 days	7,1 fold ↑	11 fold ↑
Atazanavir 300 mg/Ritonavir 100 mg q.d., 8 days	10 mg, single dose	3,1 fold ↑	7 fold ↑
Lopinavir 400 mg/Ritonavir 100 mg B.I.D., 17 days	20 mg q.d., 7 days	2,1 fold ↑	5 fold ↑
Gemfibrozil 600 mg b.i.d., 7 days	80 mg, single dose	1,9 fold ↑	2,2 fold ↑
Eltromobopag 75 mg q.d. , 10 days	10 mg, single dose	1,6 fold ↑	2 fold ↑
Darunavir 600 mg/Ritonavir 100 mg b.i.d., 7 days	10 mg q.d., 7 days	1,5 fold ↑	2,4 fold ↑
Tipranavir 500 mg/Ritonavir 200 mg b.i.d., 11 days	10 mg, single dose	1,4 fold ↑	2,2 fold ↑
Dronedaron 400 mg b.i.d.	No data	1,4 fold ↑	No data
Itraconazol 200 mg q.d. , 5 days	10 mg or 80 mg, single dose	1,4 fold ↑	1,4 fold ↑
Ezetimibe 10 mg q.d. , 14 days	10 mg q.d. , 14 days	1,2 fold ↑	1,2 fold ↑
Fosamprenavir 700 mg/Ritonavir 100 mg b.i.d., 8 days	10 mg, single dose	↑ 8%	1,5 fold ↑
Aleglitazar 0,3 mg, 7 days	40 mg, 7 Days	↔	1,1 fold ↑
Silymarin 140 mg t.i.d., 5 days	10 mg, single dose	↔	↔
Fenofibrat 67 mg t.i.d., 7 days	10 mg, 7 Days	↑ 7%	1,2 fold ↑
Rifampicin 450 mg q.d. , 7 days	20 mg, single dose	↔	↔

m Source: Swiss Compendium and translated into the English by the Swiss site : www.compendium .ch

Interacting Drug, dosage and treatment period	Rosuvastatin-dosage and treatment period	Effect on rosuvastatin AUC	Effect on rosuvastatin-C max
Ketoconazol 200 mg b.i.d., 7 days	80 mg, single dose	↑ 2%	↔
Fluconazol 200 mg q.d., 11 days	80 mg, single dose	↑ 14%	↔
Erythromycin 500 mg q.i.d., 7 days	80 mg, single dose	28% ↓	31% ↓
Baicalin 50 mg t.i.d., 14 Days	20 mg, Single dose	47% ↓	19% ↓

«↑»: Increase.

«↔»: No change (defined as <20% change of rosuvastatin -AUC, C-max).

«↓»: Decrease.

### 10.11 Blinding and Emergency Unblinding

The personnel involved in the conduct of the trial as well as the study participants will remain blinded to the assigned study medication, throughout the trial.

Unblinding: The study physician may decide to break the randomization code of the participant for security reasons only. Emergency code breaking instructions will be provided to the sites. In Switzerland: the coordinating centre must be informed immediately if a code has been broken.

## 11 Assessments

All assessments including screening and unplanned study visits will be recorded on the case report form (CRF) – See Appendix 22.1

### Demographic data, medical history and medication questionnaire

Patients will be questioned on details necessary for determining eligibility for entry into the trial and important study variables. Topics to be covered include, age, gender, race, presence of CVD risk factors (smoking status, family history of CVD etc.), past medical history, current medications and the presence of any allergies.

The questionnaire will be completed by a study investigator at the screening visit. At all subsequent visits patients will be asked:

1. If they have developed or been diagnosed with any new medical illnesses since the last review
2. If they have started or stopped any non-study medications
3. Their current smoking status.

### Compliance assessment

1. Compliance with the study medication will be performed at two time points (Weeks 48 and 96) to estimate compliance throughout the study. A self-assessment question sheet and VAS will be used asking participants to estimate compliance over the last fortnight and month. (See appendix 22.2)

### Physical examination

Consists of:

1. Complete physical examination
2. Blood pressure measurement with patient sitting

3. Recording presence of bilateral lower limb peripheral pulses of the posterior tibial and the dorsalis pedis arteries
4. Anthropometry
  - a. Weight will be measured in kilograms (kg) with patient clothed; footwear removed
  - b. Height will be measured in metres (m) with footwear removed
  - c. Waist circumference (adapted from the International Diabetes Federation guidelines on the diagnosis and management of the metabolic syndrome)
    - i. Subject should be standing erect dressed in underwear; all outer clothing should be removed.
    - ii. Make sure the tape does not compress the tissues during the measurement.
    - iii. Record the measurement after the subject has exhaled with the tape measure in a horizontal plane, midway between the inferior margin of the ribs and the superior border of the iliac crest.

### **Electrocardiogram (ECG)**

ECG will be performed by trained study investigators at screening visit.

All ECGs will be read by a blinded study doctor; all important abnormalities on the ECG will be reported. Specifically the presence of findings consistent with prior myocardial infarction (as defined by the 2007 Joint European Society of Cardiology/American College of Cardiology Federation/American Heart Association/World Health Federation (ESC/ACCF/AHA/WHF) Task Force;

- Any Q-wave in leads V2-V3  $\geq 0.02s$  or QS complex in leads V2 and V3
- Q-wave  $\geq 0.03s$  and  $\geq 0.1mV$  deep or QS complex in leads I, II, aVL, aVF or V4-V6, in any two leads of a contiguous lead grouping (I, aVL, V6; V4-V6; II, III, aVF)
- R-wave  $\geq 0.04s$  in V1-V2 and R/S  $\geq 1$  with a concordant positive T-wave in the absence of a conduction defect

